2.5 Analysis of the primary objective

2.5.1 Primary endpoint

The primary variable is the change from baseline (baseline definition as in [section 2.1.1](#)) to 3 years in the CogState Global Cognitive Composite Score (GCCS). The CogState cognitive test battery includes the following seven tasks:

1. **Detection Test (DET)** – Assesses psychomotor function using the speed (milliseconds) of correct responses in a simple reaction time paradigm
2. **Identification Test (IDT)** – Assesses visual attention using the speed (milliseconds) of correct responses in a simple reaction time paradigm
3. **Continuous Paired Associate Learning (CPAL)** – Assesses visual episodic memory measuring accuracy of performance by the number of errors made over 6 learning trials
4. **One back (ONB)** - Assesses working memory using the speed (milliseconds) of correct responses in a n-back paradigm
5. **International Shopping List Test (ISLT)** – Assesses verbal learning using the accuracy (number of words recalled correctly) of recall in a verbal list learning paradigm
6. **International Shopping List Test – delayed recall (ISLT-DR)** - Assesses verbal memory using the accuracy (number of words recalled correctly) of delayed recall in a verbal list learning paradigm
7. **Groton Maze learning Test (GMLT)** – Assesses executive function using the number of total errors (number of error responses over 5 trials) in a hidden pathway maze learning paradigm

Standardized z-scores for each outcome measure and visit will be calculated using the sample baseline mean and standard deviation of individual tasks as follows:

- $Z_{DET} = - (\text{Log}_{10}(\text{DET}) - \text{baseline mean of } \text{log}_{10}(\text{DET}))/\text{SD of } \text{log}_{10}(\text{baseline DET}),$
- $Z_{IDT} = - (\text{Log}_{10}(\text{IDT}) - \text{baseline mean of } \text{log}_{10}(\text{IDT}))/\text{SD of } \text{log}_{10}(\text{baseline IDT}),$
- $Z_{CPAL} = - (\text{CPAL total errors} - \text{baseline mean of CPAL total errors}/\text{SD of baseline CPAL total errors}),$
- $Z_{ONB} = - (\text{Log}_{10}(\text{ONB}) - \text{baseline mean of } \text{log}_{10}(\text{ONB}))/\text{SD of } \text{log}_{10}(\text{baseline ONB}),$
- $Z_{ISLT} = (\text{ISLT} - \text{baseline mean of ISLT})/\text{SD of baseline ISLT},$
- $Z_{ISLT-DR} = (\text{ISLT-DR} - \text{baseline mean of ISLT-DR})/\text{SD of baseline ISLT-DR},$
- $Z_{GMLT} = - (\text{GMLT} - \text{baseline mean of GMLT})/\text{SD of baseline GMLT}$

Note that negative sign is included in the calculation for tasks where increasing values indicate worsening performance (i.e., Z_{DET} , Z_{IDT} , Z_{CPAL} , Z_{ONB} and Z_{GMLT}) so that for all standardized change scores negative values indicate a decline from baseline while positive scores indicate improvement from baseline.

These seven individual z-scores are then combined to generate the GCCS:

CogState GCCS = average of (Z_{DET} , Z_{IDT} , Z_{CPAL} , Z_{ONB} , Z_{ISLT} , $Z_{ISLT-DR}$, Z_{GMLT})

The composite score will be computed if at least five of the seven tests are completed and the five tests provide an assessment of the three cognitive domains as defined below being assessed. That is, a composite score requires that each cognitive domain be measured by at least one cognitive test.

In addition to the GCCS, composite scores for three main subdomains memory, attention and psychomotor function will also be generated by combining the standardized change from baseline scores for individual tests from the CCB using the following formulae:

- Composite score of memory tests = average of (Z_{CPAL}, Z_{ISLT}, Z_{ISLT-DR})
- Composite score of executive function tests = average of (Z_{ONB}, Z_{GMLT})
- Composite score of attention tests = average of (Z_{DET}, Z_{IDT})

Each composite score will be the average of the non-missing individual test z-scores.

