### **9.4 Analysis of the primary variable(s)**

#### **9.4.1 Variable(s)**

The primary variable is the change from baseline to 3 years in the CogState Global Cognitive Composite Score (GCCS). The CogState cognitive test battery includes the following seven tasks:

1. Detection Test (DET) – Assesses psychomotor function using the speed (milliseconds) of correct responses in a simple reaction time paradigm
2. Identification Test (IDT) – Assesses visual attention using the speed (milliseconds) of correct responses in a simple reaction time paradigm
3. Continuous Paired Associate Learning (CPAL) – Assesses visual episodic memory measuring accuracy of performance by the number of errors made over 6 learning trials
4. One back (ONB) - Assesses working memory using the speed (milliseconds) of correct responses in a n-back paradigm
5. International Shopping List Test (ISLT) – Assesses verbal learning using the accuracy (number of words recalled correctly) of recall in a verbal list learning paradigm

6. International Shopping List Test – delayed recall (ISLT-DR) - Assesses verbal memory using the accuracy (number of words recalled correctly) of delayed recall in a verbal list learning paradigm
7. Groton Maze learning Test (GMLT) – Assesses executive function using the number of total errors (number of error responses over 5 trials) in a hidden pathway maze learning paradigm

Standardized z-scores for each outcome measure and visit will be calculated using the sample baseline mean and standard deviation of individual tasks as follows:

- $Z_{DET} = - (\text{Log}_{10}(\text{DET}) - \text{baseline mean of } \text{log}_{10}(\text{DET}))/\text{SD of } \text{log}_{10}(\text{baseline DET}),$
- $Z_{IDT} = - (\text{Log}_{10}(\text{IDT}) - \text{baseline mean of } \text{log}_{10}(\text{IDT}))/\text{SD of } \text{log}_{10}(\text{baseline IDT}),$
- $Z_{CPAL} = - (\text{CPAL total errors} - \text{baseline mean of CPAL total errors})/\text{SD of baseline CPAL total errors},$
- $Z_{ONB} = - (\text{Log}_{10}(\text{ONB}) - \text{baseline mean of } \text{log}_{10}(\text{ONB}))/\text{SD of } \text{log}_{10}(\text{baseline ONB}),$
- $Z_{ISLT} = (\text{ISLT} - \text{baseline mean of ISLT})/\text{SD of baseline ISLT},$
- $Z_{ISLT-DR} = (\text{ISLT-DR} - \text{baseline mean of ISLT-DR})/\text{SD of baseline ISLT-DR},$
- $Z_{GMLT} = - (\text{GMLT} - \text{baseline mean of GMLT})/\text{SD of baseline GMLT}$

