2.6 Analysis of secondary efficacy objective(s)

2.6.1 Secondary endpoints

The secondary efficacy variables are –

1. Change from baseline in individual cognitive domains (memory, executive function, and attention) as assessed by the individual components of the cognitive assessment battery at 3 years.
2. Change from baseline in the summary score of the instrumental activities of daily living (IADL) as assessed with Functional Activity Questionnaire (FAQ) at 3 years.

Composite scores for three main subdomains memory, attention and psychomotor function will also be generated by combining the standardized change from baseline scores for individual tests from the CCB using the following formulae:

- Composite score of memory tests = average of (Z_{CPAL} , Z_{ISLT} , $Z_{ISLT-DR}$)
- Composite score of executive function tests = average of (Z_{ONB} , Z_{GMLT})
- Composite score of attention tests = average of (Z_{DET} , Z_{IDT})

Each composite score will be the average of the non-missing individual test z-scores.

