3.3 Blinded sample size re-estimation

Approximately 520 patients will be randomized in order to provide overage to account for the information loss caused by an estimated 30% "drop-out" (including death, lost-to-follow-up, permanent discontinuation of study medication and start of treatments for AD or cognitive impairment) during 3 year period. In the PET imaging substudy approximately 430 patients will be randomized.

A loss of 30% of information is a crude estimate therefore it is planned to monitor the 'dropout' pattern as the trial is ongoing in order to provide a better prediction of the information loss for a given number of patients. The final number of patients randomized may be reduced if there is sufficient evidence that the information loss will be less than 30% and that the precision of the estimates of treatment effect (as described in the sample size section above), will be maintained.

4 Change to protocol specified analyses

Not applicable

5 Appendix

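### SAP 2.5.1 misplaces a bracket in the CPAL formula, so as written one of the seven components of the primary endpoint is not standardised

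*SAP*

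**What the plan says.** The SAP introduces the seven task scores in section 2.5.1 with a general rule: "Standardized z-scores for each outcome measure and visit will be calculated using the sample baseline mean and standard deviation of individual tasks". The formula for CPAL then reads, inside its brackets, "CPAL total errors} - \text{baseline mean of CPAL total errors}/\text{SD of baseline CPAL total errors". (The backslashes and braces are mark-up from the text form of the PDF.) The closing bracket comes after the SD.

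Protocol 9.4.1 gives the same score as "CPAL total errors} - \text{baseline mean of CPAL total errors})/\text{SD of baseline CPAL total errors", with the bracket closed before the division.

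The score is then used in two places:

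- The primary endpoint, SAP 2.5.1: "These seven individual z-scores are then combined to generate the GCCS". Missing tests are tolerated: "The composite score will be computed if at least five of the seven tests are completed", provided that each of the three domains is covered by at least one test. Composites average the non-missing scores.
- A secondary endpoint, SAP 2.6.1, in the line beginning "Composite score of memory tests = average of", where CPAL is one of three components.

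SAP section 4, headed "Change to protocol specified analyses", is marked as not applicable.

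**The concern.** Under ordinary operator precedence, the SAP formula subtracts a constant (mean divided by SD) from the raw error count and reverses the sign. The result is not a z-score. This conflicts with the SAP's own rule for all seven tasks, with the six neighbouring formulas (including GMLT, the other error-count task), with protocol 9.4.1, and with the statement that nothing departs from the protocol.

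The formula defines part of the primary endpoint in version 5.0 of the SAP, the version dated just before database lock. If a programmer followed it literally, the GCCS would no longer be an equally weighted average of seven standardised tests. The main conclusion rests on Cohen's d, which is scale-free, so the headline result would not show that the composite had been mis-scaled. The tipping-point analysis in SAP 2.5.5 would also be affected. It multiplies imputed GCCS values by 95% or 105% according to their sign, so its penalty depends on where zero lies on the scale.

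**Working it through.** **Inputs.** The two formulas come from SAP 2.5.1 and protocol 9.4.1. Write X for CPAL total errors, and m and s for their baseline mean and SD. Neither document gives m or s, so the values below are assumptions chosen to show a range. There is no stated figure to reproduce.

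**Step 1: compare the formulas.**

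| | SAP as printed | Protocol |
|---|---|---|
| Score | −(X − m/s) | −(X − m)/s |
| Baseline mean | −m(1 − 1/s) | 0 |
| Baseline SD | s | 1 |
| Change, CPAL present at both visits | −(X_t − X_0) | −(X_t − X_0)/s |
| Effect on GCCS of a 1-SD worsening | −s/7 | −1/7 = −0.143 |

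The constant m/s cancels from the change, but the missing division by s does not. The two versions agree only if s = 1. A simulation at m = 10, s = 5 gave a printed score with mean −8.0 and SD 5.0, matching −10(1 − 1/5) = −8, and a protocol score with mean 0 and SD 1.

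**Step 2: weight of CPAL at baseline.** Let the other tests have SD 1 and let all pairs have correlation r. CPAL's share of composite variance is its covariance with the composite divided by the composite's variance:

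- GCCS: (s² + 6rs) / (s² + 6 + 12rs + 30r)
- Memory: (s² + 2rs) / (s² + 2 + 4rs + 2r)

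For example, at s = 5 the GCCS share is 25/31 = 81% with r = 0, and (25 + 15)/(25 + 6 + 30 + 15) = 40/76 = 53% with r = 0.5.

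| Assumed s | GCCS share, r from 0.5 to 0 | Memory share, r from 0.5 to 0 |
|---|---|---|
| 1 (intended) | 14% | 33% |
| 2 | 27–40% | 55–67% |
| 5 | 53–81% | 79–93% |
| 10 | 72–94% | 89–98% |

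CPAL reaches half of the GCCS variance when s² = 6 + 30r, that is at s = 2.4, 3.9 and 4.6 for r = 0, 0.3 and 0.5.

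**Step 3: weight in change scores.** The tests need not change with equal variability. If CPAL's standardised change SD is 0.5 to 1.5 times that of the other tests, the same formula with s multiplied by 0.5 to 1.5 gives GCCS shares of 14–60%, 33–90% and 53–97% at s = 2, 5 and 10. The intended share under the same variation is 4–27%.

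**Step 4: CPAL missing at one visit only.** Suppose an average patient has no true change and misses CPAL only at follow-up. The printed formula gives a baseline GCCS of −m(1 − 1/s)/7. The follow-up GCCS, averaged over the other six tests, is 0. The apparent gain is m(1 − 1/s)/7:

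- m = 5, s = 2: 2.5/7 = 0.36
- m = 10, s = 5: 8/7 = 1.14

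Under the protocol formula the gain is 0.

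**The case against.** The strongest reply is that this is a misprint with an obvious meaning. The line sits under a rule that calls for standardised scores and among six correctly bracketed formulas. The SAP says that it details the analyses agreed in the protocol, and the protocol prints the right version. A competent programmer would probably code it correctly, and a baseline score without mean 0 and SD 1 should be caught in routine checks. All of this stands, and it means that the harm is conditional on literal coding, of which the documents give no sign. They do not show that the derivation was checked either: the change log mentions a dry-run review, but not of the GCCS.

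The figures of 0.36 and 1.14 are shifts for one patient, not for the treatment difference. If CPAL is missing at similar rates in the two arms, the mean shift largely cancels and mainly noise remains. That also stands. The documents give no frequency for the pattern. CPAL missing at baseline may be uncommon, because the battery is also given at screening and Visit 103 and earlier values may be carried in.

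The size has no anchor in the documents, so the ranges are wide. The direction does not depend on them: CPAL is over-weighted for any SD above 1.

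Finally, a slip in converting the PDF to text cannot be fully excluded. The brackets in the printed line balance, which makes a true misprint more likely, but the line should be compared with the PDF.

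**Conclusion.** The concern holds. As written, the SAP formula does not standardise CPAL and contradicts both the protocol and the SAP's own rule. The intended formula is clear, so this is a drafting error and not a choice of method. Its consequence, if coded literally, is that CPAL's weight in the GCCS and the memory composite is multiplied by its raw baseline SD. At an assumed SD of 5, CPAL would make up 53–81% of baseline GCCS variance instead of 14%, and 79–93% of the memory composite instead of 33%. These figures rest on assumed SDs and on a common inter-test correlation of 0 to 0.5. The sample size, stated in units of Cohen's d, is not affected. The correction should be made because the line defines the primary endpoint, even though correct programming is more likely than not.

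**What to change.** In SAP 2.5.1, close the bracket before the division, so that Z_CPAL = −(X − m)/s, where X is CPAL total errors and m and s are their baseline mean and SD, as in protocol 9.4.1. Compare the line with the PDF first.

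Before database lock, confirm that the dataset specification and the program use this form. A sufficient check is that baseline Z_CPAL has mean 0 and SD 1 in the sample used for standardisation, like the other six scores. The cost is one bracket and one check of a derived variable.

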2.5.2 Statistical hypothesis, model, and method of analysis

The change from baseline in the GCCS of CogState test battery will be analyzed using a repeated measures analysis of covariance (ANCOVA) model in which treatment, age stratification factor, MMSE stratification factor, education level, APOE4 status (carrier vs. non-carrier), baseline cerebrovascular disease burden, visit (Weeks 26, 52, 78, 104, 130 and Week 156) and treatment-by-visit interaction are included as fixed-effect factors and baseline GCCS and visit-by-baseline GCCS interaction as covariates, with a common unstructured covariance matrix among visits between treatment groups. The adjusted mean changes at 3 years (Week 156) within each treatment, the difference in mean changes at 3 years (Week 156) between the two treatments, and its 95% confidence interval obtained from the above model will be presented. In addition, the treatment difference (LCZ696-valsartan) in mean changes from baseline to 3 years will also be expressed based on a standardized effect size (Cohen's d) with a 2-sided 95% confidence interval. The Cohen's d will be estimated by using the adjusted between-treatment mean difference, divided by the estimated pooled standard deviation. The estimated standard deviation for the mean difference is:

$$SD = \left(\frac{1}{n_1} + \frac{1}{n_2} \right)^{1/2} \hat{\sigma}$$

where n1 and n2 are the number of patients within each treatment group and $\hat{\sigma}$ is the pooled standard deviation of the within treatment group adjusted mean change. Cohen's d can be rewritten in terms of t value of the estimated between treatment group difference based on the adjusted mean changes from the model mentioned above:

$$t = \frac{\hat{\mu}_1 - \hat{\mu}_2}{SD} = \frac{\hat{\mu}_1 - \hat{\mu}_2}{\left(\frac{1}{n_1} + \frac{1}{n_2} \right)^{1/2} \hat{\sigma}}$$

$$\hat{d} = \frac{\hat{\mu}_1 - \hat{\mu}_2}{\hat{\sigma}} = \left(\frac{1}{n_1} + \frac{1}{n_2} \right)^{1/2} \times t$$

Confidence interval (CI) of Cohen's d is based on 95% CI of the noncentrality parameter of t value divided by the square root of the degrees of freedom from the estimated between treatment group adjusted mean change (Cumming and Finch 2001). The analysis is based on a direct likelihood method with an assumption of missing at random (MAR) for the missing data mechanism.

As the primary analysis, the repeated measure ANCOVA model will be performed in the Safety set including 'on-treatment' data (section 2.1.1) collected prior to the start of treatments for AD or cognitive impairment. The Cohen's d based on the adjusted difference in mean changes at 3

years (Week 156) between two treatments and its 95% confidence interval from this model will be used to draw the main conclusion for the primary objective. As defined in [section 2.1.1](#), on-treatment data refer to cognitive test data collected while patients are on-study-medication (regardless of treatment interruption) or within three months after final study drug intake date.

When above mentioned model does not converge, the primary analysis model will be modified by replacing the common unstructured covariance matrix with a compound symmetry covariance matrix between treatment groups and provide above mentioned estimates. If convergence issue remains after implementing the compound symmetry covariance matrix, the model will be simplified by removing baseline cerebrovascular disease burden as explanatory factor from the model.

